##### **Missing month only**

- The day will be treated as missing and both month and day will be replaced according to the above procedure.

##### **Missing day only**

- If the month and year are same as the year and month of the date of the first dose double-blind study drug, then the date of the first dose double-blind study drug will be assigned to the missing day.
- If either the year is before the year of the date of the first dose of double-blind study drug or if both years are the same but the month is before the month of the date of the first dose of double-blind study drug, then the last day of the month will be assigned to the missing day.
- If either the year is after the year of the date of the first dose of double-blind study drug or if both years are the same but the month is after the month of the date of the first dose of double-blind study drug, then the first day of the month will be assigned to the missing day.

If the stop date is complete and the imputed start date as above is after the stop date, the start date will be imputed by the stop date.

#### **6.4.2. Missing Date Information for Prior or Concomitant Medications**

For prior or concomitant medications, including rescue medications, incomplete (ie, partial missing) start date and/or stop date will be imputed. When the start date and the stop date are both incomplete for a subject, impute the start date first.

#### **6.4.2.1. Incomplete Start Date**

The following rules will be applied to impute the missing numerical fields. If the stop date is complete and the imputed start date is after the stop date, then the start date will be imputed using the stop date.

##### **Missing day and month**

- If the year of the incomplete start date is the same as the year of the date of the first dose of double-blind study drug, then the day and month of the date of the first dose of double-blind study drug will be assigned to the missing fields.
- If the year of the incomplete start date is prior to the year of the date of the first dose of double-blind study drug, then December 31 will be assigned to the missing fields.
- If the year of the incomplete start date is after the year of the date of the first dose of double-blind study drug, then January 1 will be assigned to the missing fields.

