## 5.3. Demographic and Baseline Characteristics

Subject demographic and disease characteristics (age, age group (6-11, 12-17, and  $\geq 18$  years), gender, race, ethnicity, height, weight, body mass index, six minute walk distance, six minute walk distance groups ( $<300$  meters,  $\geq 300$ - $<400$  meters,  $\geq 400$  meters), time to run/walk 10 meter, time to stand from supine, time to stand from supine ( $<5s$ ,  $\geq 5s$ ), performance of Upper Limb Assessment (PUL), corticosteroid use (Yes/No), and ambulatory/non-ambulatory) at study entry will be summarized for overall subjects, a subgroup of subjects with corticosteroid use duration ( $<12$  months,  $\geq 12$  months) at baseline, a subgroup of subjects with corticosteroid type (deflazacort vs prednisone/prednisolone) at baseline, and a subgroup of ambulatory/non-ambulatory subjects at study entry.

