### 5.8.4. Timed Function Tests

Timed function test data (ie, time to stand from supine, time to run/walk 10 meters, time to climb 4 stairs, and time to descend 4 stairs) and change from baseline to each post baseline visit will be summarized descriptively by visit for ambulatory subjects with non-missing baseline timed function tests assessments. Similarly the time to stand from supine, time to run/walk 10 meters, time to climb 4 stairs, and time to descend 4 stairs will also be summarized for each actual age.

Timed function test (TFT) data imputation rules as the following will be used in the summary.

- If time to run/walk 10 meters > 30 sec, then set to 30 sec.
- If time to stand from supine > 30 sec, then set to 30 sec.

The Kaplan-Meier method will be applied to the analysis of age at loss of ambulation. The median age at loss of ambulation will be reported by treatment group in studies 020/020e (ataluren/ataluren, placebo/ ataluren, and overall), corticosteroid use duration (<12 months,  $\geq$ 12 months), and corticosteroid type (deflazacort vs prednisone/prednisolone) at baseline. The Kaplan-Meier curves will also be displayed. The age at loss of ambulation is defined as age of the disease progression reported as the adverse event. The subjects who are ambulatory at the end of study or discontinuation will be censored on the last valid visit date. Age on that date will be used in the analysis.

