##### **Missing day only**

- If the month and year of the incomplete start date are the same as the month and year of the date of the first dose of double-blind study drug, then the day of the date of the first dose of double-blind study drug will be assigned to the missing day.
- If either the year is before the year of the date of the first dose of double-blind study drug or if both years are the same but the month is before the month of the date of the first dose of double-blind study drug, then the last day of the month will be assigned to the missing day.
- If either the year is after the year of the date of the first dose of double-blind study drug or if both years are the same but the month is after the month of the date of the first dose of double-blind study drug, then the first day of the month will be assigned to the missing day.

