### **8.2. Matched Populations**

To compare CINRG with Study 020e, the matched populations are defined in the following table for different endpoints and analyses.

Endpoint/Analysis	Age (Years) at Study Entry	Age (Years) at Assessment	Steroid Use	Ambulation status	Exclude EXON 51 and 45	Baseline value	Visit Year
Age at loss of ambulation	7-14	Not applicable	Cumulative Steroid use duration at each assessment $\geq 6$ months	Ambulatory at study entry	Yes		Not applicable
Piece-wise regression based on FVC	Not applicable	$\leq 19$	Cumulative Steroid use duration at each assessment $\geq 24$ months	Non-ambulatory at each assessment	Yes	Not applicable	$\geq 2012$
%-predicted FVC	7-15	Not applicable	Not applicable	Non-ambulatory at study entry	Yes		Not applicable
%-predicted FEV1	7-15	Not applicable	Not applicable	Non-ambulatory at study entry	Yes		Not applicable
PEF	7-15	Not applicable	Not applicable	Non-ambulatory at study entry	Yes		Not applicable
6MWT	7-15	Not applicable	Cumulative Steroid use duration at each assessment $\geq 6$ months	Ambulatory at study entry	Yes		Not applicable
time taken to run/walk 10 meters	7-15	Not applicable	Cumulative Steroid use duration at each assessment $\geq 6$ months	Ambulatory at study entry	Yes		Not applicable
time taken to stand from supine	7-15	Not applicable	Cumulative Steroid use duration at each assessment $\geq 6$ months	Ambulatory at study entry	Yes		Not applicable
NSAA	7-15	Not applicable	Cumulative Steroid use duration at each assessment $\geq 6$ months	Ambulatory at study entry	Yes		Not applicable

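### Year-only corticosteroid start dates before dosing are imputed to the latest possible date, which shortens steroid duration and can misplace boys near the 12-month subgroup cut and the 24-month FVC filter

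*SAP*

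**What the plan says.** SAP 6.4.2 covers every medication: "For prior or concomitant medications, including rescue medications, incomplete (ie, partial missing) start date and/or stop date will be imputed". It has no separate rule for corticosteroids, although SAP 5.5 and Protocol 10.4.2 single them out for attention.

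For a start date lacking day and month, SAP 6.4.2.1 has three branches:
- Year before the first dose: "prior to the year of the date of the first dose of double-blind study drug, then December 31 will be assigned to the missing fields".
- Same year as the first dose: "then the day and month of the date of the first dose of double-blind study drug will be assigned to the missing fields".
- Later year: "then January 1 will be assigned to the missing fields".

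If only the day is missing and the month precedes the first dose, "then the last day of the month will be assigned to the missing day". Under 6.4.2.2, a year-only stop date in a year before the last dose also goes to 31 December.

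Steroid duration is then used as a number:
- SAP 5.3 tabulates baseline data for "a subgroup of subjects with corticosteroid use duration" below 12 months and 12 months or more.
- SAP 5.8.4 uses the same split for Kaplan-Meier age at loss of ambulation ("The median age at loss of ambulation will be reported by treatment group in studies 020/020e", and by steroid duration and type). SAP 8.3 uses the 12-month split again.
- SAP 8.2 filters on "Cumulative Steroid use duration at each assessment": at least 6 months for five of the nine rows, at least 24 months for the piece-wise FVC regression, and no steroid filter for the other three.

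The only Study 020e algorithm that SAP 8.3 carries over to CINRG is NSAA scoring.

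**The concern.** Assigning the latest pre-dose date is harmless when the question is whether a drug was prior or concomitant. It is a poor way to start a clock. For a boy already on steroids at first dose, the imputed duration can equal the true duration or fall short of it, never exceed it, so the errors do not average out.

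Protocol 6.4.1 calls corticosteroids the only drug treatment with demonstrated benefit in DMD. Steroid duration is therefore a natural explanatory factor for age at loss of ambulation, and the 12-month split exists to show it. If boys with more than a year of use are moved below the cut, the contrast is blurred. In the FVC comparison the same error decides which Study 020e assessments are admitted.

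The rule also refers to double-blind study drug, which is not given in this open-label extension. The first dose meant could be that of Study 020, taken literally, or of 020e, if the phrase came from a template. The choice decides which boys are misplaced.

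**Working it through.** The documents give no figure for this point, so there is none to reproduce.

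**Inputs.** Study 020 dosing began on 10 April 2013, recruitment was to last about 18 months, and double-blind treatment lasted 48 weeks = 336 days (Protocol 1.1). **Assumptions.** First doses F are spread evenly over 10 April 2013 to 9 October 2014 (548 days); the 020e baseline is B = F + 336 days; the true start is uniform over the dates compatible with the record; use is continuous. Cuts are 183, 365 and 730 days. All percentages are of boys with a year-only start in the stated year.

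**Mean shortening.**
- Earlier year: (365 − 1)/2 = 182 days, about 6 months, range 0 to 12.
- Same year, anchor on day n of the year: (n − 1)/2. Mean n is about 186 for F and 176 for B, giving about 92 and 88 days, or 3 months.
- Day only missing: about 15 days.

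**12-month cut, anchor = Study 020 first dose.**
- Same-year start: imputed duration at B is always 336 days, below 365. The boy is misplaced if he really started at least 365 − 336 = 29 days before F, a share of (n − 29)/n when n > 29. For F = 10 April 2013 (n = 100) that is 71%. Averaged over the window it is about 75%.
- Prior-year start: imputed duration is n + 336, below 365 only if n ≤ 28, that is 28 of 548 dose days. About 5% are misplaced.

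**12-month cut, anchor = 020e first dose.** B runs from 12 March 2014 to 10 September 2015; let m be its day of the year.
- Same-year start: truly below 12 months, so none is misplaced.
- Prior-year start: imputed duration is m days, below the cut unless B is 31 December. The true duration is at least 365 days for m of the 365 possible dates. Mean m = 176, and 176/365 = 48%.

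| Start year relative to anchor | 020 anchor | 020e anchor |
|---|---|---|
| Same year | about 75% | 0% |
| One year before | about 5% | about 48% |
| Two or more years before | 0% | 0% |

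Every misplacement in the table is downward.

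**24-month FVC filter, 020 anchor** (wrongly below 24 months at Weeks 0, 24, 48, 72):
- One year before: 43%, 47%, 10%, 0%.
- Same year: 0%, 7%, 59%, 0%.
- Two years before: 5% at Week 0, then none.

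**6-month CINRG filter.** Under the 020 anchor a continuous user who began before Study 020 has at least 336 imputed days at 020e entry, so none is misplaced. Under the 020e anchor, 42%, 20% and 2% of prior-year starts are misplaced at Weeks 0, 12 and 24.

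**Midpoint of the possible interval instead.** Mean bias falls to about 0. Misplacement at 12 months falls from about 75% to 17% for same-year starts (020 anchor; about 1.5% down and 15.6% up). It falls from 48% to 29% for prior-year starts (020e anchor), split roughly evenly.

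**The case against.** The strongest reply is that this is small. The study has no formal hypothesis (SAP 3.4), the paired t-tests were dropped (SAP 7), and the CINRG comparison is outside the CSR (SAP 1). What remains for the CSR is a baseline table and descriptive Kaplan-Meier medians. Year-only steroid dates may also be few. All of that stands and limits the weight of the point. It does not supply a duration rule, and the 12-month split in 5.8.4 is in the CSR.

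The rule also does not always shorten. A later-year start goes to 1 January and is lengthened by a mean of 182 days. A same-year start that really followed the first dose is lengthened by about 90 days. Late stop dates lengthen completed courses. For cumulative use with interruptions the net direction is therefore not fixed. The one-directional error holds for continuous use begun before dosing.

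A reader might infer three stronger claims that the documents do not support:
- That the CINRG filters are compromised generally. Under the literal anchor the 6-month filter is untouched for continuous users who began before Study 020, and three rows have no steroid filter.
- That the ataluren side of the FVC comparison carries more steroid exposure than CINRG. The SAP does not say how CINRG partial dates are handled, so the direction of any bias is not established.
- That the below-12-month group is mostly long-term users. Its make-up depends on the unknown number of year-only dates, and starts two or more years before the anchor year never fall into it by this rule.

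**Conclusion.** The point holds in limited form. For steroid use begun before dosing, SAP 6.4.2.1 shortens year-only durations by a mean of about 6 months (earlier year) or 3 months (same year), and nothing else in the SAP says how duration is derived. Only boys near a cut are misplaced: at 12 months, about 75% of same-year starts or about 48% of prior-year starts, depending on the anchor. Under the literal anchor, the 24-month FVC filter is exposed at entry and at the visits up to about Week 48, and no longer by Week 72.

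These shares rest on uniform start dates, continuous use and an even spread of first doses. They apply to affected records only; the share of all boys cannot be worked out from the documents. The effect is on descriptive subgroup results and one external comparison, not on the primary safety analysis. A correction is worth making because the error is systematic and cheap to remove.

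**What to change.** In SAP 6.4.2:
- Keep the current rule solely for classifying medications as prior or concomitant.
- For corticosteroid duration (5.3, 5.8.4, 8.2, 8.3), impute a partial start to the midpoint of the interval compatible with the record. For use ongoing at first dose, that interval runs from the earliest possible date to the earlier of the latest possible date and the first dose.
- State whether the anchor is the Study 020 or the 020e first dose.
- Apply the same duration rule to CINRG.
- Report how many steroid start and stop dates are partial, by data source.
- Repeat the 12- and 24-month classifications with the earliest and the latest possible dates. At 12 months the earliest-date bound errs upward (about 19% of same-year starts under the 020 anchor, 52% of prior-year starts under the 020e anchor), so the two bounds bracket the answer.

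A fixed 1 July date capped at first dose would not be enough. For first doses up to 1 July (83 days in 2013 plus 182 in 2014 = 265 of 548, or 48% of the assumed window) it returns the first-dose date, and same-year starts keep 336 days.

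The cost is SAP wording, one derived date and a small sensitivity table. No new data are needed.

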##### **Missing month only**

- The day will be treated as missing and both month and day will be replaced according to the above procedure.

##### **Missing day only**

- If the month and year of the incomplete start date are the same as the month and year of the date of the first dose of double-blind study drug, then the day of the date of the first dose of double-blind study drug will be assigned to the missing day.
- If either the year is before the year of the date of the first dose of double-blind study drug or if both years are the same but the month is before the month of the date of the first dose of double-blind study drug, then the last day of the month will be assigned to the missing day.
- If either the year is after the year of the date of the first dose of double-blind study drug or if both years are the same but the month is after the month of the date of the first dose of double-blind study drug, then the first day of the month will be assigned to the missing day.

#### **6.4.2.2. Incomplete Stop Date**

The following rules will be applied to impute the missing numerical fields. If the date of the last dose of double-blind study drug is missing, replace it with the last visit date or data cut-off date if the subject is on-going. If the imputed stop date is before the start date (imputed or non-imputed start date), then the imputed stop date will be equal to the start date.

##### **Missing day and month**

- If the year of the incomplete stop date is the same as the year of the date of the last dose of double-blind study drug, then the day and month of the date of the last dose of double-blind study drug will be assigned to the missing fields.
- If the year of the incomplete stop date is prior to the year of the date of the last dose of double-blind study drug, then December 31 will be assigned to the missing fields.

- If the year of the incomplete stop date is after the year of the date of the last dose of double-blind study drug, then January 1 will be assigned to the missing fields.

#### **Missing month only**

- The day will be treated as missing and both month and day will be replaced according to the above procedure.

#### **Missing day only**

- If the month and year of the incomplete stop date are the same as the month and year of the date of the last dose of double-blind study drug, then the day of the date of the last dose of double-blind study drug will be assigned to the missing day.
- If either the year is before the year of the date of the last dose of double-blind study drug or if both years are the same but the month is before the month of the date of the last dose of double-blind study drug, then the last day of the month will be assigned to the missing day.
- If either the year is after the year of the date of the last dose of double-blind study drug or if both years are the same but the month is after the month of the date of the last dose of double-blind study drug, then the first day of the month will be assigned to the missing day.

## **7. ANALYSIS CHANGES FROM PROTOCOL**

The supportive analyses on 6-minute walk test have been removed because they are not of the scientific interest any more after the early termination of the study. All paired t-tests have been removed.

## **8. CINRG DATA**

### **8.1. Overview of CINRG Data**

CINRG is a natural history registry database which collects DMD data using consortium of medical and scientific investigators from academic and research centers on neuromuscular disease. Demographics and baseline characteristics, corticosteroids medication use (and type), efficacy endpoints including 6MWT, time taken to stand from supine, time taken to run/walk 10 meters, NSAA, spirometry, and EK will be analyzed. Other endpoints collected by CINRG but not in Study 020e will not be included into this analysis plan. The CINRG natural history control (data transferred on November 18, 2016) will be compared to ataluren's efficacy data to assess the ataluren's long-term treatment benefit.

### **8.2. Matched Populations**

To compare CINRG with Study 020e, the matched populations are defined in the following table for different endpoints and analyses.

Endpoint/Analysis	Age (Years) at Study Entry	Age (Years) at Assessment	Steroid Use	Ambulation status	Exclude EXON 51 and 45	Baseline value	Visit Year
Age at loss of ambulation	7-14	Not applicable	Cumulative Steroid use duration at each assessment $\geq 6$ months	Ambulatory at study entry	Yes		Not applicable
Piece-wise regression based on FVC	Not applicable	$\leq 19$	Cumulative Steroid use duration at each assessment $\geq 24$ months	Non-ambulatory at each assessment	Yes	Not applicable	$\geq 2012$
%-predicted FVC	7-15	Not applicable	Not applicable	Non-ambulatory at study entry	Yes		Not applicable
%-predicted FEV1	7-15	Not applicable	Not applicable	Non-ambulatory at study entry	Yes		Not applicable
PEF	7-15	Not applicable	Not applicable	Non-ambulatory at study entry	Yes		Not applicable
6MWT	7-15	Not applicable	Cumulative Steroid use duration at each assessment $\geq 6$ months	Ambulatory at study entry	Yes		Not applicable
time taken to run/walk 10 meters	7-15	Not applicable	Cumulative Steroid use duration at each assessment $\geq 6$ months	Ambulatory at study entry	Yes		Not applicable
time taken to stand from supine	7-15	Not applicable	Cumulative Steroid use duration at each assessment $\geq 6$ months	Ambulatory at study entry	Yes		Not applicable
NSAA	7-15	Not applicable	Cumulative Steroid use duration at each assessment $\geq 6$ months	Ambulatory at study entry	Yes		Not applicable

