### 8.3. Analyses Based on Matched Populations of CINRG and Study 020e

Demographics and baseline characteristics (age, race, ambulation status, corticosteroid use (yes or no), duration of corticosteroid use, corticosteroid type, baseline 6MWD, baseline time to run/walk 10 meters, baseline time to stand from supine, baseline %-predicted FEV1, %-predicted FVC, PEF, NSAA total score) will be summarized descriptively for CINRG and Study 020e

based on each matched population. The summary will be displayed by corticosteroid use (yes vs no) and cumulative steroid use ( $\geq 12$  months vs  $< 12$  months) for baseline ambulatory and non-ambulatory subjects separately. The baseline is defined as the first visit in CINRG data. The comparison to the natural history data (ie, CINRG data) based on matched subjects will be performed in FVC using piece-wise regression models and age to loss of ambulation using Kaplan-Meier method.

Piece-wise regression models will be applied to log FVC in CINRG and study 020e data, separately, using different ages as the changepoint. The most possible changepoint in terms of age will be chosen at the best model fit (ie, AICC value is the maximal). Scatter plots of log FVC and the most fitted piece-wise regression line will be generated for CINRG and study 020e, separately. Comparison between the observed and predicted FVC in study 020e will be performed using repeated measures analysis of variance to account for within-subject correlation, where the predicted values are based on the regression equation estimated by the best fit regression model based on CINRG data.

In study 020e, the loss of ambulation is defined as the disease progression reported as the adverse event or the time to run/walk 10 meters  $> 30$  seconds, whichever occurs earlier. The event age is the one on the AE start date. The subjects who are ambulatory at the end of study will be censored on the last valid timed function tests assessment date. Age on that date will be used in the analysis. In the CINRG data, the age at the earliest report of the non-ambulation or the time to run/walk 10 meters  $> 30$  seconds, whichever earlier, will be picked as the event age. If subjects in CINRG data do not report non-ambulation, the age at the last report of ambulation will be chosen as the censor age. A sensitivity analysis will be performing based on the loss of ambulation defined only by disease progression AE.

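### The CINRG 'matched' populations are formed by restriction only, and neither comparison with Study 020e describes adjustment for baseline function, so residual imbalance of unknown direction cannot be separated from a treatment effect

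*SAP*

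**What the plan says.** SAP 8.1 gives the purpose: "The CINRG natural history control (data transferred on November 18, 2016) will be compared to" the ataluren efficacy data, in order to assess long-term treatment benefit. SAP section 1 places this analysis outside the CSR.

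In SAP 8.2, "the matched populations are defined in the following table for different endpoints and analyses". Each row sets cohort-level criteria:

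- an age range, at entry or at assessment;
- a minimum cumulative steroid duration for some endpoints (6 months for loss of ambulation, 24 months for piece-wise FVC);
- ambulation status, for example "Ambulatory at study entry" for loss of ambulation;
- "Exclude EXON 51 and 45" in every row;
- visit year 2012 or later, for piece-wise FVC only.

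A column headed "Baseline value" is marked not applicable for piece-wise FVC. In the text extracted from the PDF it is blank for the other eight rows.

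SAP 8.3 says the comparison with CINRG "will be performed in FVC using piece-wise regression models and age to loss of ambulation using Kaplan-Meier method". It also lists baseline characteristics, including "duration of corticosteroid use, corticosteroid type, baseline 6MWD, baseline time to run/walk 10 meters", time to stand, percent-predicted FVC and FEV1, PEF and NSAA. These are to be summarised descriptively by cohort.

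**The concern.** Restriction makes two cohorts eligible on the same terms. It does not balance them within those terms. Two statements in the Protocol show why that matters here. Section 13.4.2 says that worsening timed function tests correlate with time to wheelchair dependency, so baseline function is prognostic for the endpoint being compared. Section 2.1 says that most boys use a wheelchair by 10 to 14 years of age. A band of ambulatory boys aged 7-14 at entry therefore mixes boys who are years from losing ambulation with boys close to it.

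The cohorts also enter differently. Boys in 020e had to complete treatment in a 48-week trial (Protocol 4.2), and their baseline is the last valid assessment up to the first extension dose (SAP 6.2). The CINRG baseline is the first registry visit (SAP 8.3).

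At stake is the reading of a gap between two curves. With no adjustment, the same gap could come from the drug, from a difference in function at entry, or from both.

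**Working it through.** **No figure to reproduce.** The documents state no cohort size, event count, alpha, power or effect size for the CINRG comparison. SAP 3.4 says the study size rests on no formal hypothesis. What follows sets the text side by side and then illustrates size. Every numerical input to the illustrations is assumed.

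**Step 1. What each comparison conditions on.**

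| Comparison (SAP 8.3) | Restriction (SAP 8.2) | Covariates in the analysis |
|---|---|---|
| "age to loss of ambulation using Kaplan-Meier method" | age 7-14 at entry, steroids at least 6 months, ambulatory, exon | none named |
| Observed 020e FVC against CINRG prediction | age at most 19 at assessment, steroids at least 24 months, non-ambulatory, exon, visit year | age, with a changepoint |

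The repeated-measures step for FVC handles within-subject correlation, not confounding. The functional covariates appear only in descriptive tables, with no balance threshold and no stated consequence of imbalance.

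**Step 2. Continuous covariate, true hazard ratio 1.** Let 020e be better by d SD, with log-hazard b per SD. The contrast exp(-b x d) is

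- exp(-0.7 x 0.3) = 0.81 and exp(-1.0 x 0.3) = 0.74;
- exp(-0.7 x 0.5) = 0.70 and exp(-1.0 x 0.5) = 0.61.

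An unadjusted comparison shows less than this, because omitting a strong covariate pulls the hazard ratio towards 1. The unadjusted values were simulated with a normal covariate, exponential hazards, 20,000 per group and 50-100% of subjects having events. A repeat run fell inside every range:

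| d | b = 0.7 | b = 1.0 | Overall |
|---|---|---|---|
| 0.3 SD | 0.81-0.86 | 0.78-0.83 | 0.78-0.86 |
| 0.5 SD | 0.74-0.78 | 0.68-0.73 | 0.68-0.78 |

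**Step 3. Direction.** For a binary covariate, let p1 and p0 be the shares with poor function in 020e and CINRG, and h its hazard ratio. The spurious ratio at the start of follow-up is [1 + p1(h-1)] / [1 + p0(h-1)].

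- 40% against 60%: 1.4/1.6 = 0.875 (h = 2), 1.8/2.2 = 0.818 (h = 3), 2.2/2.8 = 0.786 (h = 4).
- 60% against 40%: 1.6/1.4 = 1.143, 1.8 and 2.2 reversed give 2.2/1.8 = 1.222, and 2.8/2.2 = 1.273. This is bias against ataluren.

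**Step 4. Does restriction remove it, and does adjustment?** The simulation used 150 replicates and 150 boys per cohort, all ambulatory at entry and aged 7 to under 15, with delayed entry handled and no drug effect. Age at loss of ambulation had mean 12.5 and SD 2.2 years, chosen to fit Protocol 2.1. The function score was 250 + 45 x years to loss, with noise SD 60. Only 020e was selected, by a floor on that score.

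| Mean function difference | Unadjusted HR | HR adjusted for function and entry age | Shift in median age at loss |
|---|---|---|---|
| 0 m | 0.99 | 1.00 | -0.04 y |
| 19 m | 0.81 | 1.07 | 0.48 y |
| 40 m | 0.59 | 1.08 | 1.18 y |
| 67 m | 0.34 | 0.94 | 2.21 y |

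This score is a direct noisy measure of time to the event, so the table shows the mechanism and does not estimate its size in these data. Both cohorts met the age and ambulation limits and the bias remained. Adjustment brought the ratio close to 1, with 4-6% two-sided rejections.

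**The case against.** - **The blank cells may be lost text.** Unused cells elsewhere in the table are marked not applicable, so a blank in the "Baseline value" column need not mean that no criterion exists. This stands: the documents as extracted do not show that the loss-of-ambulation row lacks a baseline range. A range would still be restriction, and for FVC the cell is explicitly not applicable.
- **Function is not wholly ignored.** Ambulatory status is a coarse functional criterion, and the descriptive tables could reveal imbalance. Both are true, but neither changes the comparison itself.
- **No imbalance has been shown.** A reader might infer that 020e enrolled milder boys and that the comparison therefore overstates benefit. The documents do not support that. They hold no CINRG baseline data. The entry rule requires completed treatment, not preserved function, and non-ambulatory entrants are planned for. In the earlier programme 173 of 174 boys went on to the extension (Protocol 2.2.3). That was a different trial, but it gives no sign of strong selection among completers.
- **The analysis has low formal weight.** It is outside the CSR, carries no alpha, and the primary objective is safety. For loss of ambulation SAP 8.3 plans curves, not a hazard ratio or test, so the ratios above only measure how far the curves could separate. This limits the urgency. It does not answer the point, because SAP 8.1 still names treatment benefit as the purpose.

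**Conclusion.** The point holds in a limited form. The populations are restricted, not matched, and the two specified comparisons describe no adjustment for baseline function. Residual imbalance therefore cannot be told apart from a treatment effect. Its size and direction are unknown, and it may favour or disfavour ataluren. The illustrative ranges, 0.78-0.86 at 0.3 SD and 0.68-0.78 at 0.5 SD, rest on an assumed log-hazard of 0.7-1.0 per SD, assumed imbalances and a true null. They show that moderate imbalance could matter, not that it exists.

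Two further readings should be avoided. The plan cannot be said to lack any baseline-value restriction, given the blank cells. Nor does the point reach every row of the table, because SAP 8.3 specifies a comparison between cohorts only for FVC and loss of ambulation.

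This should be changed because the remedy is cheap, but it does not affect the CSR analyses.

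**What to change.** Keep the SAP 8.2 table as the eligibility step, and complete or explain the blank cells.

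**Loss of ambulation.**
- Prespecify propensity-score weighting (overlap or inverse-probability) or covariate adjustment on entry age, steroid type and duration, 10-metre run/walk time, time to stand and 6MWD.
- SAP 5.8.4 recognises an ataluren/ataluren group, whose members had the 48-week double-blind treatment before their 020e baseline. Weighting on that baseline could remove real effect. For these boys take the covariates, and the start of follow-up, from double-blind study entry. Apply the ambulatory criterion at that point too, so that a loss during those 48 weeks counts as an event. Having completed the double-blind study remains a selection condition, to be stated as a limitation.
- Handle delayed entry on the age scale.
- Report standardised differences before and after weighting, and weighted curves with robust intervals. Keep the unweighted curves as sensitivity.

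**FVC.** Add available covariates such as steroid type and duration to the CINRG prediction model, or state that the comparison is descriptive.

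If none of this is done, call the populations restricted.

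**Cost.** SAP wording, modest programming and some loss of effective sample size. How much depends on overlap between the cohorts and on the completeness of the CINRG covariates, neither of which the documents report.
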